### **Assessment of the nasal mucosa infiltrate**

Determination of the percentage of infiltrating cells in the nasal mucosa will be carried out with samples obtained from a swab introduced into each nostril of the volunteer and the cells obtained will be placed on a slide, followed by their fixation with methanol (99% Synth), and then stained in hematoxylin, for later analysis by an experienced pathologist.

### **Determination of the concentration of IgAs and antimicrobial peptides**

The salivary concentration of IgAs and the antibacterial peptides [LL-37 (cathelicidin), defensin-1, lactoferrin, and lysozyme] will be determined using ELISA commercial kits (Biosay Technology Laboratory, Shanghai, China), in accordance with the manufacturer's instructions.

### **Determination of cytokine concentration**

The concentration of cytokines IL-1β, IL-1ra, IL-4, IL-5, IL-6, IL-10, IL-12p70, IL13, IL-17A, and TNF-alpha, both in serum, saliva, as in the whole blood culture supernatant, stimulated or not with LPS (Lipopolysaccharide), will be determined by using LEGENPlex for human cytokines, which is based on a bead system (BioLegend, San Diego, CA, USA), following manufacturer's instructions. The cytokine concentrations will be calculated from the

values of their respective standard curves, obtained at the same time as the evaluation of the samples.

### Immune cell immunophenotyping

Evaluation of the number, type, and activation profile of NK cells and T lymphocytes will be carried out with blood samples collected in tubes containing EDTA anticoagulant that will be mixed 1:1 with Ficoll-Paque (density gradient 1077, FicollPaqueTM PLUS, GE Healthcare, Sweden). After centrifugation for 30 minutes at 2000 rpm, the cell pool, corresponding to the fraction of mononuclear cells will be collected, counted, and  $1 \times 10^5$  cells will be added in 1.5 mL conical tubes. Then, these cells will be washed with MACSBuffer [PBS (1x) containing bovine serum albumin (0.5%) and EDTA (2 mM)]. After this step, the cells will be incubated with a mix of monoclonal antibodies to evaluate the type, concentration, and activation profile of these cells, as shown in Table 1, by using the antibodies to the surface molecules: CD3, CD4, CD8, CD16, CD27, CD38, CD45, CD56, CD70, CD197, and HLA-DR.

**Table 1.** Description of the panel of antibodies to be used in immunophenotyping of NK cells and T lymphocytes.

Type	Profile	Surface Markers		
T Lymphocytes	Activation	CD3+	CD4+ CD8+	CD38+ CD38+ HLA-DR+ HLA-DR+
	Naive	CD3+	CD4+ CD8+	CD27+ CD27+ CD45RA+ CD45RA+ CD197+ CD197+
	Central Memory	CD3+	CD4+ CD8+	CD27+ CD27+ CD45RA- CD45RA- CD197+ CD197+
	Effector Memory	CD3+	CD4+ CD8+	CD27- CD27- CD45RA- CD45RA- CD197- CD197-
Natural Killer Cells		CD3+	CD16+	CD56+

Data acquisition will be performed using a BD Canto cytometer (Becton Dickinson Immunodiagnostic System, San Jose CA, USA). The definition of the gates will be based on the analysis of the FMO (Fluorescent Minus One).

### **Cytotoxicity Assay of NK cells**

The *in vitro* assessment of the activity of NK cells will be carried out by using the commercial kit NKVUE tubes, which allows for evaluating the activity of NK cells through the production of interferon-gamma (Nederby, 2018). In addition, the cytotoxic activity of NK cells will be also assessed by using another test, which will be initiated by the isolation of these cells from peripheral blood using the commercial Invitrogen Dynabeads Untouched Human NK Cell kit (Thermo Fisher Scientific, Invitrogen, Vienna, Austria), which allows the isolation of these cells by negative selection. Then, using the commercial kit NKTEST, we will evaluate the cytotoxic activity of NK cells isolated by mixing these with K562 target cells, in a ratio of 5:1 and 2:1, following the manufacturer's guidelines.

### **Determination of the systemic concentration of BDNF and hormones**

Serum levels of BDNF (pg/mL), cortisol (ngmL-1), and hGH (mLU mL-1) will be determined using ELISA commercial kits [BDNF Quantikine ELISA kit (Catalog number: SBD00); Cortisol ELISA EIA-1887 (Catalog number: SKGE008B; hGH ELISA EIA-3552 (Catalog number: SG100) R&D System, Inc. USA]. In addition, serum levels of sex hormones [progesterone (pg/mL), estrogen (pg/mL), and testosterone (pg/mL)] will also be determined by ELISA commercial kits [Testosterone Parameter Assay Kit (Catalog number: SKGE010), Estradiol Parameter Assay Kit (Catalog number: KGE014), Human Total Progesterone ELISA (Catalog number: DYC5415-5), R&D System, Inc. USA]. It is noteworthy to clarify that these parameters will be evaluated in all volunteers (both in men and women groups), whilst, in particular, the data obtained in the evaluation of the sexual hormones progesterone and estrogen also will be used to define the phase of the menstrual cycle in which each female volunteer of the study will be during the five different occasions proposed in the present study. All evaluations will follow the manufacturers' guidelines.

### **Assessments of upper airway symptoms**

The WURSS-21 questionnaire (Wisconsin Upper Respiratory Symptom Survey – 21 items) (Annex 1) will be used to assess the occurrence of upper airway symptoms. This instrument is composed of 21 questions, in which the first question is associated with the individual's perception of "how sick do you feel today?", followed by 10 questions based on specific

symptoms of the cold condition, more 9 questions related to the impact of cold symptoms in the individual's quality of life, and one last question comparing the current status of the cold symptoms with the previous day. All items will be scored on a Likert scale ranging from 0 to 7 (from 0 = no symptoms to 7 = severe).

The severity of the upper airway symptoms will be measured from the sum of the scores of all the days in which it was evaluated, with the final score divided by the number of days in which there were reports of symptoms. In terms of the severity in relation to the interference in the volunteer's quality of life, it will be obtained the sum of the scores of all the days in which there was a report, and the final score will be divided by the number of days with symptoms. In addition, to analyze the percentage of incidence of the group, the number of days with symptoms of each group will be calculated, adjusting for the number of volunteers in the group. Then, the adjusted values of each group will be added, considering this value as 100%, from which the percentage of each group will be calculated.

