### **SECONDARY**

Evaluate the effect of daily intake of fermented milk containing 40 billion LcS on both systemic immune/inflammatory and upper airway responses, as well as the incidence and duration of upper airway symptoms, and also on mood states in amateur triathletes participating in this study, before and after an official triathlon competition.

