### **Anamnesis, physical examination, and competition**

At the beginning of the study, all participants will undergo an anamnesis with a cardiovascular and otorhinolaryngological analysis to exclude the presence of cardiovascular diseases and upper airway symptoms resulting from rhinosinusitis, rhinopathies, or any other pre-existing alteration in these systems. In addition, the WURSS (Wisconsin Upper Respiratory Symptom Survey) questionnaire will be used to verify the occurrence of upper airway symptoms not only during this period but also throughout the study period (Annex 1), and the presence of premenstrual syndrome will be self-reported by the female volunteers during the anamnesis.

It is noteworthy to cite that the volunteers will be oriented to maintain their usual daily routine, including sleep, diet, and training/physical activity during the study performance. In this respect, to characterize not only the quality of life (Annex 2) but also the level of physical activity (Annex 3), questionnaires will be applied with open questions about the participants' lifestyle and habits, history and current habits of physical activity, as well as participation in competitions. Beyond these questionnaires, it will be also assessed the occurrence of discomfort or gastrointestinal problems related to the daily intake of fermented milk containing LcS or not by using a questionnaire with open questions about gastrointestinal problems will be used (Annex 4). The volunteers who reported any gastrointestinal discomfort during the ingestion of the fermented milk containing or not LcS will be oriented to immediately interrupt this ingestion and seek medical assistance. In case of the volunteer needs to interrupt the ingestion of fermented milk for five consecutive days, following medical recommendation, this volunteer and its data will be excluded from the study.

It is utmost of importance to point out that all athletes will have medical follow-ups by [name] [name], a specialist in Sports Medicine, throughout the study. Besides, through social media, all volunteers will be able to directly contact not only [name] but also other researchers involved in the study's development in order to communicate any adverse events and other unintended effects of trial interventions.

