### **Sample collection**

Blood, saliva, and nasal swab will be collected on five different occasions: (1) before the beginning of the ingestion of fermented milk containing LcS or placebo; (2) 24 hours before the triathlon competition; (3) immediately (IM); (4) 72 hours (post-72h); and (5) 14 days after the competition, as shown in Figure 1. In addition, on the same occasions, the occurrence of upper airway symptoms and mood states will also be assessed by using questionnaires.

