### **Statistical analysis**

All data obtained during the development of this study will be added to a unique file, preferentially in an Excel file, which will be available to all researchers not only to consult and check the data quality/accuracy but also to add any results through GOOGLE-DRIVE. It is noteworthy to clarify that, to perform all the statistical analysis proposed here, we will follow the "intention-to-treat" (ITT) analysis, not only because it is recommended as an analysis strategy for randomized studies but also to be possible to maintain the sample size, as well as to use the data obtained from the participants regardless of whether they complete the study since ITT considers all randomized participants in the analysis, whether they drop out or not. In addition, the multiple imputation (MI) method will be applied to handle missing data since

MI fills in missing values by generating plausible numbers derived from distributions of and relationships among observed variables in the data set. Beyond these analyses, in order to check and increase the reliability of the results obtained in the ITT analysis, we also intend to conduct the statistical analysis regarding the per-protocol (PP) analysis, which will be used exclusively the complete data obtained from the volunteers.

After all data will be added to the Excel file and the data quality/accuracy is checked by the researchers, these data will be initially compared with the Gaussian curve, and normality determined for each variable.

If the variable presents a parametric behavior, the mean and standard deviation will be used, and they will be compared by using the ANOVA test for repeated measures with post hoc tests for intragroup (longitudinal) and intergroup (cross-sectional) analysis.

On the other hand, if the data present a non-parametric behavior, they will be represented by median and interquartile ranges, and they will be compared by using Friedman's test with Müller-Dun post hoc test for intragroup (longitudinal) and the Kruskal-Wallis test with Müller Dunn's post hoc test for intergroup (cross-sectional).

Using Pearson (for parametric values) or Spearman tests (for non-parametric values), the correlation between the variables studied will be evaluated.

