In addition, the McNemar Chi-square test (with Yates correction) will be used to determine whether the difference in the number of volunteers who presented or not upper airway symptoms, as well as in the duration of the symptoms, is significantly different in each group (paired analysis). Additionally, Chi-square test will be used to perform the same analysis but between the volunteer groups (unpaired analysis).

A risk of less than to 0.05 ( $p<0.05$ ) will be considered statistically significant for every study.

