#### **SCHEDE OF ACTIVITIES TO BE DEVELOPED**

Parameters	Enrollment	Allocation	Intervention				
			Pre-Triathlon		Post-Triathlon		
Timepoint			-60d to -30d	-30d	-1d	0d	3d
Recruitment and selection of volunteers	X						
Informed consent	X						
Anamnesis, anthropometry, cardiopulmonary test	X						
Randomization		X					
Intervention: LcS/Placebo intake			X	X	X	X	X
Questionnaire - WURSS	X			X		X	X

Questionnaire - IPAQ	X			X			
Questionnaire - gastrointestinal problems	X			X		X	X
Questionnaire – SF36	X			X		X	X
Questionnaire – BRUMS	X			X		X	X
Questionnaire - Subjective Perception of Effort Scale	X				X		
Blood, saliva, nasal swab collection			X	X	X	X	X

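### The upper-airway incidence percentage is a share of symptom-days, not incidence, and symptom duration is assigned categorical tests with no categories defined

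*Combined protocol and SAP*

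**What the plan says.** The secondary objective covers "the incidence and duration of upper airway symptoms" (Objectives, Secondary).

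Under Assessments of upper airway symptoms, the group's incidence percentage starts from the number of days with symptoms in each group, adjusted for the number of volunteers in that group. The next step reads: "the adjusted values of each group will be added, considering this value as 100%, from which the percentage of each group will be calculated".

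Under Statistical analysis, a McNemar test with Yates correction is applied within each group to "the difference in the number of volunteers who presented or not upper airway symptoms, as well as in the duration of the symptoms". Between groups, "Chi-square test will be used to perform the same analysis but between the volunteer groups (unpaired analysis". No cut-point or set of categories for duration appears anywhere. The same section has a general rule for non-normal variables: Friedman's test with a "post hoc test for intragroup (longitudinal) and the Kruskal-Wallis test with" a further post hoc procedure between groups. That rule is not assigned to duration.

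The recording frequency is described in two ways. Anamnesis, physical examination, and competition uses the questionnaire "to verify the occurrence of upper airway symptoms not only during this period but also throughout the study period". The work plan also says throughout the study, and Annex I is laid out as a daily report. Sample collection ties it to the five sampling visits: "on the same occasions, the occurrence of upper airway symptoms and mood states will also be assessed by using questionnaires". The schedule of activities has a row "Questionnaire - WURSS" marked only in visit columns.

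**The concern.** Incidence is the proportion of athletes who develop symptoms. The quantity defined here does not contain the number of athletes affected. A reader who sees an incidence of 40% against 60% would take those as risks, when they are two parts of a total that is 100% by construction. The printed figure could disagree with the plan's own comparison of athletes with and without symptoms, and both would appear in the report as results for the same endpoint.

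For duration, McNemar and chi-square tests need categories. If duration is a number of days, as the symptom-day wording suggests, the plan does not say how days become categories. Two analysts following the text could report different results.

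**Working it through.** **The plan's own figure.** The plan gives no number for the symptom endpoint. Its only calculated figure is N = 62 for salivary IgA. With noncentrality f²·N·m/(1−ρ) = 0.0225 × 62 × 5 / 0.5 = 13.95 and 4 and 240 degrees of freedom, power is 0.857 (0.844 at N = 60), so 62 reproduces. Nothing below depends on it.

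**Inputs.** Arm size is 35 to 40 (Population and design of the study). All symptom counts below are assumed, and they suppose daily recording.

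**The share.** Let D be the symptom-days in an arm and n its volunteers. The rule gives

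share₁ = (D₁/n₁) / (D₁/n₁ + D₂/n₂).

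This depends only on the ratio of mean symptom-days. Four consequences follow, the last three with 35 per arm:

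- *Level lost.* 0.4 against 0.6 days per athlete gives 0.4/1.0 = 40%. 4 against 6 days gives 4/10 = 40%.
- *Equal incidence, unequal share.* 10 ill in each arm, for 3 and 6 days: 30/35 = 0.857 and 60/35 = 1.714, so 33.3/66.7. Risks are 28.6% in both arms.
- *Unequal incidence, equal share.* 10 ill for 1 day against 2 ill for 5 days: 10/35 = 0.286 in both arms, so 50/50. Risks are 10/35 = 28.6% and 2/35 = 5.7%, a difference of 22.9 points (Newcombe 95% CI 5.1 to 39.9). Fisher p = 0.023, chi-square 0.011 uncorrected and 0.026 with Yates. With 40 per arm the share is still 50/50, and risks are 25.0% and 5.0% (Fisher p = 0.025).
- *Order reversed.* 5 ill for 14 days against 10 ill for 3 days: 70/35 = 2.0 and 30/35 = 0.857, so 70/30. Observed risks run the other way, 14.3% and 28.6%.

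**Duration.** Take 35 per arm with 10 ill in each and 25 at zero. Arm 1 has 3, 4, 5, 5, 6, 6, 7, 7, 8, 9 days (60 in total). Arm 2 has 1, 1, 2, 2, 3, 3, 4, 4, 5, 5 days (30). If duration is split at a cut-point:

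| Cut | Athletes at or above | Fisher p | Yates p |
|---|---|---|---|
| ≥1 day | 10 v 10 | 1.0 | 1.0 |
| ≥4 | 9 v 4 | 0.22 | 0.22 |
| ≥5 | 8 v 2 | 0.084 | 0.088 |
| ≥6 | 6 v 0 | 0.025 | 0.033 |
| ≥7 | 4 v 0 | 0.11 | 0.12 |

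At ≥1 day the test only repeats incidence. The plan names Yates for McNemar but is silent for the between-group test. Uncorrected chi-square gives 0.040, 0.010 and 0.039 at ≥5, ≥6 and ≥7.

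**Checking the obvious replacement.** On the same data, Kruskal-Wallis with zeros included gives p = 0.56, although means are 60/35 = 1.71 and 30/35 = 0.86 days. Among the 20 symptomatic athletes it gives p = 0.002. The two analyses answer different questions.

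**The case against.** The share is a labelling fault. It is a one-to-one function of the ratio of mean symptom-days, it drives no p-value, and the Statistical analysis section separately compares the number of volunteers with symptoms. All of that stands. A reader might infer that the incidence test itself is invalid, but the documents do not support this: the comparison of athletes with and without symptoms is a proper one. The tie and the reversal also need constructed data. They show what the rule permits, not what is likely.

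On duration, a reader might infer that a cut-point will be picked after seeing the data. The plan says nothing of the kind. The chi-square could be meant for duration categories or even for group totals of days. What the text supports is that the method is unspecified, and the p-values by cut apply to one reading of it.

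A reader might also escalate this to the primary endpoint, because the ethics opinion names symptom occurrence as primary. That opinion describes 60-70 participants and a 2024 race, against 70-80 and 2025 in the protocol, so it appears to summarise a different version. The protocol's abstract and objectives agree that salivary IgA is primary and symptoms are secondary.

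Finally, the day-count examples should not be carried over to visit-only recording, because the documents do not settle how many WURSS-21 occasions follow baseline.

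**Conclusion.** The point holds for a secondary endpoint. Followed exactly, the rule prints a relative symptom-day burden under the name of incidence. This follows from the formula and needs no assumption. How far the figure could mislead depends on assumed counts: in the illustration, 50/50 is printed where risks differ by 22.9 points. The planned test of occurrence and the salivary IgA sample size are unaffected.

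The duration analysis is incompletely specified. That duration means days is an inference from the symptom-day wording, but any measure in days would need categories before these tests could be used. If a cut-point is used, the result depends on it: in the example, Fisher p ranges from 1.0 to 0.025.

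**What to change.** 1. Delete the 100% share, or relabel it relative symptom-day burden and print absolute symptom-days per athlete beside it.
2. Report incidence per arm as athletes with at least one symptomatic record divided by athletes randomised, with a risk difference and 95% CI. Use the between-group chi-square test already planned, or Fisher's exact test, and state whether a correction is applied.
3. Replace McNemar and chi-square for duration with an analysis of the number of days. State the target before unblinding. One option is total symptomatic days per athlete, zeros included. This combines occurrence and length, and a rank test on it is weak when most values are zero, so means should be shown. The other is length among symptomatic athletes. That is a post-randomisation subset, so it should be descriptive.
4. Reconcile whether WURSS-21 is recorded daily or throughout (Anamnesis, work plan, Annex I) or only at visits (Sample collection, schedule of activities). If only at visits, call the outcome symptomatic occasions, not days.

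None of this needs extra participants or samples. If recording is already daily, or the outcome is renamed, it is a change of wording. If day counts are wanted and recording is only at visits, a diary over the 44 ingestion days, at the 5 to 7 minutes per questionnaire given in the ethics opinion, would take 44 × 5 = 220 to 44 × 7 = 308 minutes per athlete, about 3.7 to 5.1 hours.

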### **Assessment of mood state**

The Brunel mood scale (BRUMS, Annex 6) will be used to assess the mood state. The BRUMS involves 24 mood indicators, divided into six subitems, namely anger, confusion, depression, fatigue, tension, and vigor. The volunteer should indicate on a scale from 0 (zero) to 4 (four) what they are feeling on the time-point of application of the BRUMS. (Rohlf, 2008).

### **Statistical analysis**

All data obtained during the development of this study will be added to a unique file, preferentially in an Excel file, which will be available to all researchers not only to consult and check the data quality/accuracy but also to add any results through GOOGLE-DRIVE. It is noteworthy to clarify that, to perform all the statistical analysis proposed here, we will follow the "intention-to-treat" (ITT) analysis, not only because it is recommended as an analysis strategy for randomized studies but also to be possible to maintain the sample size, as well as to use the data obtained from the participants regardless of whether they complete the study since ITT considers all randomized participants in the analysis, whether they drop out or not. In addition, the multiple imputation (MI) method will be applied to handle missing data since

MI fills in missing values by generating plausible numbers derived from distributions of and relationships among observed variables in the data set. Beyond these analyses, in order to check and increase the reliability of the results obtained in the ITT analysis, we also intend to conduct the statistical analysis regarding the per-protocol (PP) analysis, which will be used exclusively the complete data obtained from the volunteers.

After all data will be added to the Excel file and the data quality/accuracy is checked by the researchers, these data will be initially compared with the Gaussian curve, and normality determined for each variable.

If the variable presents a parametric behavior, the mean and standard deviation will be used, and they will be compared by using the ANOVA test for repeated measures with post hoc tests for intragroup (longitudinal) and intergroup (cross-sectional) analysis.

On the other hand, if the data present a non-parametric behavior, they will be represented by median and interquartile ranges, and they will be compared by using Friedman's test with Müller-Dun post hoc test for intragroup (longitudinal) and the Kruskal-Wallis test with Müller Dunn's post hoc test for intergroup (cross-sectional).

Using Pearson (for parametric values) or Spearman tests (for non-parametric values), the correlation between the variables studied will be evaluated.

In addition, the McNemar Chi-square test (with Yates correction) will be used to determine whether the difference in the number of volunteers who presented or not upper airway symptoms, as well as in the duration of the symptoms, is significantly different in each group (paired analysis). Additionally, Chi-square test will be used to perform the same analysis but between the volunteer groups (unpaired analysis).

A risk of less than to 0.05 ( $p<0.05$ ) will be considered statistically significant for every study.

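### Multiple imputation is paired with ANOVA and rank tests without a between-arm estimate or a pooling step; a mixed model on the observed samples should be the primary salivary IgA analysis

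*Combined protocol and SAP*

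**What the plan says.** All of this is in the Statistical analysis section unless noted.

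- Analysis set: intention-to-treat, on the ground that "ITT considers all randomized participants in the analysis, whether they drop out or not". One reason given for choosing it is "to be possible to maintain the sample size".
- Missing data: "In addition, the multiple imputation (MI) method will be applied to handle missing data". The method is explained only as follows: "MI fills in missing values by generating plausible numbers derived from distributions of and relationships among observed variables in the data set". Combining results across imputed data sets is not mentioned.
- Supporting analysis: per-protocol, "which will be used exclusively the complete data obtained from the volunteers".
- If a variable is judged normal: "ANOVA test for repeated measures with post hoc tests for intragroup (longitudinal) and intergroup (cross-sectional) analysis". The post hoc tests are not named.
- If not: "they will be compared by using Friedman's test with Müller-Dun post hoc test for intragroup (longitudinal"), with Kruskal-Wallis and a Dunn-type test between groups.
- Normality is judged variable by variable. The plan does not say whether this is done on the observed data or on each imputed set.
- Significance level: 0.05.

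Population and design of the study, exclusion criterion 6, removes any volunteer with missing data. The exclusion criteria in the ethics committee opinion repeat this rule. The section on anamnesis, physical examination and competition also excludes a volunteer, with the data, after a medically advised interruption of intake for five consecutive days.

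**The concern.** Multiple imputation gives valid inference only if the variation between imputed data sets enters the final standard error or test. Rubin's rules do this for an estimate with a standard error. The plan names tests, not estimates. Friedman, Kruskal-Wallis and Dunn procedures are reported as rank statistics and p values, which those rules do not combine directly. The normality check adds a further gap, because different imputed sets of the same variable could select different tests.

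The intention-to-treat result for salivary IgA, the primary outcome, is therefore not fully defined. Two analysts could follow the section faithfully and report different p values. If one filled-in file were analysed as though complete, the imputed values would count as measurements, standard errors would be too small, and the 5% level would not hold for the primary outcome or the continuous secondary ones.

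**Working it through.** **1. The plan's own figure.** Inputs from Population and design of the study: f = 0.15, alpha 0.05, power 0.85, 2 groups, 5 measurements, correlation 0.5, epsilon 1. For the within-between interaction:

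- lambda = f² × N × m / (1 − rho) = 0.0225 × 62 × 5 / 0.5 = 13.95
- df1 = (2 − 1)(5 − 1) = 4; df2 = (62 − 2)(5 − 1) = 240
- power = 0.857 at N = 62 and 0.844 at N = 60

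So 62 is the smallest even total that reaches 0.85, and the stated figure reproduces. It takes no account of missing data or imputation.

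**2. Which planned tests can be pooled.**

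| Planned test | Estimate with standard error? | Pooling |
|---|---|---|
| Repeated-measures ANOVA | Yes, for group-by-time contrasts | Rubin's rules; D1 for the omnibus test |
| Kruskal-Wallis, two arms | Not as reported | D2 on the chi-square, approximate |
| Friedman, Dunn post hoc | Not as reported | Not tested here |

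**3. Simulated type I error.** Null hypothesis true, N = 70, 5 occasions, correlation 0.5, normal data, monotone dropout completely at random, sequential Bayesian regression imputation, 20 imputations, 3,000 replicates, nominal level 0.05. The documents give no dropout rate, so 10%, 20% and 30% by the last occasion are assumed. Kruskal-Wallis is taken at the last occasion.

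| Analysis | 10% | 20% | 30% |
|---|---|---|---|
| Kruskal-Wallis, one imputed set as observed | 0.071 | 0.087 | 0.112 |
| Kruskal-Wallis, mean of imputations as observed | 0.078 | 0.096 | 0.131 |
| Kruskal-Wallis, pooled by D2 | 0.053 | 0.044 | 0.040 |
| ANOVA interaction, one imputed set as observed | 0.080 | 0.116 | 0.166 |
| ANOVA interaction, mean of imputations as observed | 0.081 | 0.121 | 0.169 |
| ANOVA interaction, pooled by D1 | 0.057 | 0.053 | 0.049 |
| Single change contrast, one imputed set as observed | 0.063 | 0.088 | 0.114 |
| Single change contrast, Rubin's rules | 0.047 | 0.049 | 0.043 |

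Monte Carlo error is sqrt(0.05 × 0.95 / 3000) = 0.004 near the nominal level and sqrt(0.17 × 0.83 / 3000) = 0.007 at the top of the range.

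The detail of the pooling matters too. A multivariate Wald form of the interaction test, pooled by D1 without a small-sample correction to the denominator degrees of freedom, ran at 0.078 / 0.065 / 0.074 (2,000 replicates).

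**4. Analytic cross-check for one contrast.** Let W be the within-imputation variance, B the between-imputation variance, and lambda = B / (W + B) the fraction of missing information. An estimate from one completed set has variance W + 2B, but the analysis reports W. The ratio of reported to true standard error is sqrt((1 − lambda) / (1 + lambda)), and the actual error rate is 2 × (1 − Phi(1.96 × ratio)). At assumed lambda of 0.10 / 0.20 / 0.33 the ratio is 0.90 / 0.82 / 0.71 and the error rate is 7.6% / 11.0% / 16.4%. Lambda is not the dropout rate, because correlated occasions recover some information. This therefore confirms the order of size, not the individual table entries.

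**The case against.** **The planned tests can be pooled.** A reader might infer that the intention-to-treat result cannot be validly combined at all. That is too strong. ANOVA contrasts have estimates and standard errors, and D2 held Kruskal-Wallis at 0.040 to 0.053. With two arms, Kruskal-Wallis is a rank-sum comparison, and Dunn's statistic is a mean-rank difference over its standard error, so either could be recast as a contrast. The rank branch also applies only to variables judged non-normal, and the sample size rests on the ANOVA interaction. All of this stands. What remains is that the plan chooses none of these routes.

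**Nobody says the filled-in file will be analysed as observed.** A reader might infer it from "to be possible to maintain the sample size", but that phrase gives a reason for intention-to-treat; imputation enters in the next sentence with its own rationale. The documents do not support a prediction of naive analysis. They also contain nothing that prevents it.

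**The size depends on dropout that is not given.** A reader might take the one-third from the 2022 race figures in Population and design of the study: (1858 − 1237) / 1858 = 33%. That is non-completion among all race participants, not loss of trial volunteers or samples. Failing to finish does not remove the samples taken before the race, nor by itself those at 72 hours and 14 days.

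**Under the exclusion rule there is little to impute.** If criterion 6 governs, the inflation cannot arise. That is correct, but the analysis would then no longer be intention-to-treat. The conflict has to be settled either way.

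**A paragraph on pooling would be enough.** An imputation model, a number of imputations and a named pooling rule would close the minimum gap. A mixed model is the better choice, not the only one: it uses every observed sample, needs no imputation under the same missing-at-random assumption, and yields the between-arm estimate that the plan lacks.

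**Conclusion.** The point holds as a mismatch between the missing-data method and the tests, with no between-arm estimate and no pooling step to connect them. For the two planned tests that were simulated, treating filled-in values as observed gives a type I error of about 0.07 to 0.17 at 10% to 30% dropout, against about 0.04 to 0.06 with proper pooling of the same tests. These figures assume the dropout rates, missingness completely at random and normal data; Friedman and Dunn tests were not simulated. They show what depends on the unstated step, not what the trial will do. The sample size of 62 reproduces and is not in question. The change should be made before unblinding, because it concerns the primary outcome and costs little.

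**What to change.** 1. Make the primary salivary IgA analysis a likelihood mixed model with arm, occasion and arm-by-occasion, fitted to all observed samples of all randomised athletes. Name in advance the between-arm contrast to be reported, and give it with its confidence interval. If a transformation is needed, fix it before unblinding.
2. Keep multiple imputation as a sensitivity analysis of that same contrast. State the imputation model and the number of imputations, and pool by Rubin's rules with small-sample degrees of freedom.
3. Run any rank test on observed data only, and label it so.
4. Reconcile exclusion criterion 6, and its repetition in the ethics committee opinion, with intention-to-treat, so that one rule says what happens to a participant with a missing sample. The exclusion of data after a five-day interruption of intake needs the same reconciliation.

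The cost is SAP wording and a model less familiar to the team than ANOVA. Standard software is enough, and no new data are needed.
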